Study Agent/ Intervention Description	The physical activity intervention is based on the Individual and Family Self-Management Theory (IFSMT) and includes 3 components: 1) education about the benefits of physical activity during chemotherapy; 2) guidance and resources to help the young adult set physical activity goals during chemotherapy and to self-monitor progress toward goals with a tracking device; and 3) ongoing collaboration with a physical activity coach.
Number of Subjects	75 young adults will be recruited.
Subject Participation Duration	Patients will continue in the study for approximately 12 weeks.
Duration of Follow up	No follow-up after completion of study measures at 12 weeks
Estimated Time to Complete Enrollment:	20 months
Statistical Methodology:	Descriptive statistics will be used to describe and summarize the context variables related to the sample. Variables with significant patterns of variation will be explored as potential covariates. Field notes from sessions with the coach will be recorded and organized
Safety Assessments	The Safety Monitoring Committee of the P20 Center, the Self-Management Science Center at UWM, will be responsible for monitoring the data safety of this pilot project.
Efficacy Assessments	NA
Unique Aspects of this Study	NA

SCHEMA

Study Calendar

STUDY CALENDAR						
	Visit 1 (EN)	Visit 2	Visit 3	Visit 4	Visit 5	Visit 6
All Participants						
Medical Record Review Form	X					
Individual and Family Information Form	X					
Godin Leisure Time Index	X					
Physical Activity Assessment Inventory	X					X
Self-regulation Index for Physical Activity	X					X
PROMIS-29 (Multiple symptom severity)	X					X
PROMIS-Fatigue Short Form	X					X
Wear accelerometer (Actigraph) x 1 week	X					X
Intervention Group Participants						
The facilitator will provide initial education to participants about the benefits of physical activity, setting physical activity goals, and using a physical activity tracker (Fitbit Flex).	X					
During regularly scheduled visits for chemotherapy, the facilitator will meet with participants to deliver a 30 minute intervention: 1) review physical activity summary, 2) discuss barriers and strategies to overcome barriers, and 3) revise physical activity goals as needed.		X	X	X	X	X
Physical activity visit summary report		X	X	X	X	X
Evaluation of intervention components						X
Usual Care Group Participants						

STUDY CALENDAR						

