1 SPECIFIC AIMS

Over 70,000 adolescents and young adults (AYAs) between the ages of 15 and 39 years are diagnosed with cancer each year in the United States.¹ These young patients have a unique cancer profile and frequently face months of therapy, often associated with distressing adverse side effects and decreased quality of life. Despite decades of research, fatigue remains one of the most distressing symptoms and a “major and disabling problem” for AYAs with cancer.² Persistent fatigue is implicated as one cause for the poor physical and emotional health-related quality of life outcomes in this young group of patients.³

Like many patients, AYAs receiving chemotherapy get caught in a cycle of cancer-related fatigue, which leads to decreased physical activity (PA), which contributes to deconditioning and more fatigue.⁴ An array of interventions designed to increase PA have been shown to relieve fatigue in patients with cancer receiving chemotherapy, but most of this evidence emerges from studies with middle-aged adults receiving treatment for the most common cancers. To date, no studies have tested a PA intervention to improve fatigue in AYAs receiving chemotherapy.⁵ AYAs with cancer acknowledge unmet needs for information and interventions related to PA, and AYAs report concerns about how and when to return to PA during and after treatment.⁶⁻⁹

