2 BACKGROUND

Fatigue in Adolescents and Young Adults (AYAs) with Cancer

Fatigue is one of the most prevalent and severe symptoms in adolescents and young adults (AYAs) with cancer.² Defined as “a distressing, persistent, subjective sense of physical, emotional, and/or cognitive tiredness or exhaustion related to cancer or cancer treatment that is not proportional to recent activity”²⁰ (p1), cancer-related fatigue causes significant distress for AYAs and interferes with physical activities, social function, and mood.^{2, 21} AYAs commonly report that fatigue occurs with other troubling symptoms, such as poor sleep, nausea, and pain, and within these symptom clusters, fatigue is frequently named as the priority symptom.²² AYAs with cancer have shown greater symptom severity, including fatigue, than children and older patients.^{23, 24} The higher level of fatigue in AYAs may be due to their accelerated physical and cognitive growth, hormone-related changes, as well as their involvement in multiple activities of this developmental period (school, work, relationships, and parenting).³

Cancer-related fatigue is worst during the treatment period.^{2, 25} During cycles of chemotherapy, fatigue levels may follow a predictable and fluctuating pattern of increasing in the days after each cycle but improving before the next cycle.^{2, 26} Studies also show that fatigue may be a persistent long-term problem, even for AYAs who have completed treatment.^{2, 27, 28}

Physical Activity as an Evidence-based Intervention to Manage Fatigue in AYAs

Major oncology professional organizations recommend physical activity as an evidence-based intervention to manage fatigue, although most of this evidence comes from studies with adults who have the most common cancers, such as breast and prostate cancer.²⁹ Diverse PA programs for people with cancer have included aerobic and muscle-strengthening activities, such as walking, cycling, and yoga, and most programs last between 5 and 12 weeks.³⁰⁻³³

No trials have examined a PA intervention with YAs currently receiving treatment, and minimal PA studies have been conducted with patients who have the common diagnoses of this age group, such as lymphoma, leukemia, sarcoma, and germ cell tumors. A few PA interventions have targeted young adults with cancer who have completed cancer treatment, confirming that these patients are interested and able to participate in PA programs, especially when recommended by PA experts.³⁴⁻³⁶

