Many young adults receiving cancer treatment unfortunately get caught in a cycle of cancer-related fatigue, which leads to decreased PA and physical fitness, which contributes to increased severity of fatigue and other symptoms.⁴ Studies confirm that PA declines in YAs during chemotherapy and persists into the years following cancer therapy.^{7, 17, 37, 38} In addition, YA cancer survivors acknowledge unmet needs for information and interventions related to PA.⁶⁻⁹ A recent analysis of topics and needs communicated by AYAs with cancer in an online forum suggests that YAs are interested in exercise for enjoyment, overall well-being, and weight management, but they do have concerns about safety and physical limitations and how/when to return to exercise post-treatment.⁹ AYAs with cancer cite barriers to PA similar to a healthy comparison group, such as lack of energy, lack of self-discipline, lack of skills, and no companions, but AYA cancer survivors may be less likely to cite ‘lack of time’ as a significant barrier.^{9, 17} An effective PA intervention, implemented early in the

chemotherapy treatment process, is needed to prevent the cycle of fatigue and inactivity in AYAs that is associated with negative outcomes.

Theoretical Framework

The Individual and Family Self-Management Theory (IFSMT) will be used as a framework for this study.¹⁸ This theory proposes three inter-related dimensions of context, process, and outcomes related to individuals' self-management behaviors. Contextual factors refer to the individual and family, the individual's health status, and the physical and social environment which influence self-management. The process dimension includes knowledge and beliefs, behavior-specific self-efficacy and self-regulation, and social facilitation. Outcome variables may be proximal, such as condition-specific self-management behaviors, and/or distal, such as quality of life or health care costs.

The IFSMT acknowledges the specific developmental and cancer-related needs of AYAs that influence their self-management behaviors. The intervention in this study (The "Step-Up" Study) contains three components

which target the self-management process:

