3 STUDY DESIGN

General description

The “Step-Up” Study will use a randomized experimental design to examine the preliminary efficacy of the physical activity intervention in AYAs who are receiving chemotherapy that will last approximately 12 weeks.

Number of Subjects

Seventy-five AYAs will be recruited from the Froedtert Hospital/Medical College of Wisconsin (FH/MCW) Cancer Center and Children’s Hospital of Wisconsin.

Primary Endpoints

The primary endpoints for the study include self-efficacy for physical activity, self-regulation of physical activity fatigue severity, physical activity, and fatigue severity.

The following table summarizes the proposed instruments for the study:

IFSMT factor	Variable	Measure	Pre	Post
Condition-specific: Individual	Demographics, health history, diagnosis, treatment regimen	Medical Record Review Form	x	
Condition-specific: Individual and family	Individual, household and family characteristics	Individual and Family Information Form	x	
Condition-specific: Individual	Usual amount of PA before diagnosis (self-reported)	Godin Leisure Time Index ⁴¹	x	
Process: Self efficacy	Self-efficacy for PA	Physical Activity Assessment Inventory ⁴²	x	x
Process: Goal-setting and self-monitoring	Self-regulation skills and abilities	Self-Regulation Index for PA ⁴³	x	x
Process: Negotiated collaboration	Perceptions of the intervention, preferred features of the PA tracker and facilitator	Evaluation of Intervention (intervention group only)		x
Proximal outcome: PA behaviors	# days worn, daily and weekly goals, daily step counts	PA and use of PA tracker (Fitbit) (intervention group only)	throughout	
Proximal outcome: PA behaviors	PA (steps/day)	Blinded accelerometer (ActiGraph GTx3+) x 7 days	x	x
Distal outcome: Symptom severity	Intensity of emotional distress, fatigue, pain, physical function, sleep disturbance, satisfaction with participation in social roles	PROMIS-29 ⁴⁴	x	x
Distal outcome: Fatigue severity	Fatigue frequency, duration, intensity and impact of fatigue on activities	PROMIS – Fatigue Short Form ⁴⁴	x	x

Randomization

Patients will be randomized into two groups (intervention and usual care) using the Excel 'RAND' function to create a randomization chart forcing 38 into the intervention arm and 37 into the usual care arm.

Study Timeline

Primary Completion

The study will reach primary completion 19 months from the time the study opens to accrual.

Study Completion

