Usual care group participants will meet with the facilitator who will provide initial information to participants about the study and a published flyer about general guidelines for physical activity during treatment.

3. Visits 3, 4, 5, 6 (next regularly scheduled visits for chemotherapy – at intervals of approximately 3 weeks but may range from every 2-4 weeks based on chemotherapy schedule)

Intervention group participants will meet with the facilitator who will deliver a 30 minute intervention: 1) review physical activity summary over the past weeks, 2) identify barriers and discuss strategies to overcome barriers to physical activity, and 3) revise physical activity goals as needed. The facilitator will record physical activity data from the tracking device (Fitbit Flex), discussion notes about the barriers and strategies, and physical activity

goals. Any experiences or complications that might affect physical activity will be recorded, such as hospitalizations.

Usual care group participants will meet with the facilitator to maintain engagement in the study. The facilitator will record any experiences or complications that might be pertinent to the study, such as hospitalizations and enrollment in any activities related to physical activity.

At study visit 6, all participants will complete post-study surveys and will receive instructions about wearing an accelerometer (Actigraph) for 1 week and how to return the accelerometer (Actigraph).

A study team member will contact participants after the one-week period and remind them to return the accelerometer promptly in the mailing envelope that was provided.

Following completion of the study, a member of the study team will ensure completion and return of accelerometer (Actigraph) use by all participants. All participants will receive \$25 compensation. Intervention participants will complete an additional post-study survey to evaluate components of the intervention and be invited to keep the physical activity tracker (Fitbit Flex).

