Specific Aim 1: To determine the impact of the PA intervention on the self-management process variables of self-efficacy and self-regulation, data analysis will examine differences in baseline and post-study measures of self-efficacy and self-regulation for each group. Group differences will be compared using t-tests to determine the effect of the intervention on these process variables. A mediation model will be used to describe the relationships of self-management process variables (self-efficacy and self-regulation) to PA (steps/day by accelerometer) and fatigue severity where self-efficacy and self-regulation are the main mediators of the intervention, PA is the second mediator, and fatigue severity is the dependent variable. The direct and indirect effect of treatment on PA and fatigue severity will be determined by the following steps:^{45, 46}

- Step 1. The regression of the fatigue severity on the intervention variable, ignoring the mediators, is significant.
- Step 2: The regression of the main mediators on the intervention variable is significant.
- Step 3: The regression of the second mediator (PA) on the main mediators (self-efficacy and self-regulation), controlling for the intervention, is significant.
- Step 4: The regression of the fatigue severity on the second mediator (PA), controlling for the main mediators (self-efficacy and self-regulation) and the intervention, is significant.
- Step 5: The regression of the fatigue severity on the intervention, controlling for the mediators, is non-significant and nearly-zero. In this case, the effect of intervention on fatigue severity is indirect through the mediators. If regression of the fatigue severity on the intervention, controlling for the mediators, is still significant, then the effect of treatment on fatigue severity is direct.

From the regression models, unstandardized regression coefficients and their standard errors will be calculated for the associations between the intervention variable and the mediators as well as between the fatigue severity and the mediators. The Sobel test will be used to test if the mediation effect is statistically significant.⁴⁵⁻⁴⁹ Data from field notes from the intervention group participants will be analyzed using qualitative, inductive content analysis procedures to identify themes related to self-efficacy and self-regulation skills.

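### With the process scales and fatigue surveyed together at Visit 6 and activity recorded afterwards, Steps 3 to 5 and the Sobel test cannot separate mediation from fatigue acting in reverse

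*Combined protocol and SAP*

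**What the plan says.** Section 6 (Specific Aim 1) specifies a chain from the intervention through the process variables and physical activity (PA) to fatigue: "self-efficacy and self-regulation are the main mediators of the intervention, PA is the second mediator, and fatigue severity is the dependent variable". Step 3 regresses PA on the process variables. Step 4 regresses fatigue on PA and the process variables. Step 5 then calls the intervention effect indirect if its adjusted coefficient is non-significant and close to zero, and direct if it stays significant. A Sobel test follows. The Protocol Summary makes these relationships part of the primary objective.

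The Study Calendar marks the Physical Activity Assessment Inventory, the "Self-regulation Index for Physical Activity" and the "PROMIS-Fatigue Short Form" at Visits 1 and 6 only, and the instrument table in Section 3 lists them as pre and post only. Section 5 gives the order at the end: "At study visit 6, all participants will complete post-study surveys and will receive instructions about wearing an accelerometer (Actigraph) for 1 week". The only activity data between the two time points are listed in Section 3 as "PA and use of PA tracker (Fitbit) (intervention group only"), and they do not enter the mediation model.

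Section 1 describes fatigue "which leads to decreased physical activity (PA), which contributes to deconditioning and more fatigue", and Section 2 repeats this as a "cycle of cancer-related fatigue, which leads to decreased PA and physical fitness, which contributes to increased severity of fatigue and other symptoms".

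**The concern.** Mediation analysis needs the mediator to come before the outcome. Here the main mediators and the outcome come from one survey sitting, and the second mediator is recorded in the week after the fatigue score that it is meant to explain. A regression of fatigue on these variables gives a non-zero coefficient whichever way the influence runs.

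The protocol names one reverse path itself: fatigue reduces activity. A second is a reasonable inference, namely that a tired patient rates confidence and self-regulation for activity lower. Section 2 lists low energy and low self-discipline among barriers to activity, but no section states that fatigue changes these scale scores.

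Section 6 has no lagged mediator, no stated baseline adjustment of these regressions, no reverse-path sensitivity analysis and no caveat on time order. The trial could therefore credit self-efficacy, self-regulation or activity with an improvement in fatigue that they did not cause.

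**Working it through.** **1. The plan's own figure.** Section 6 gives 68 patients for 4 predictors, a medium effect, level 0.10 and 80% power. Taking medium as f² = 0.15 (assumed), the overall regression F test has 79.6% power at 68 and needs 69 for 80%, so the figure reproduces closely. With 10% attrition, 75 × 0.9 = 67.5. This calculation concerns overall R² and says nothing about direction.

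**2. Order of measurement after baseline.**

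| Role in the model | Measure | When |
|---|---|---|
| Main mediators | Self-efficacy, self-regulation | Visit 6 survey |
| Outcome | Fatigue | Visit 6 survey |
| Second mediator | Accelerometer steps | Week after Visit 6 |

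Visits coincide with chemotherapy, and Section 2 says "fatigue levels may follow a predictable and fluctuating pattern of increasing in the days after each cycle but improving before the next cycle". The accelerometer week therefore falls in a period when fatigue may rise and hold activity down.

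**3. What the model returns under pure reversal.** Let A be arm (0/1). Let F = dA + u be Visit 6 fatigue, with u of variance 1. Let S = 0.5A − rF + √(1 − r²)e be Visit 6 self-efficacy, with e of variance 1. S has no effect on F. The 0.5 SD effect and r = 0.2 to 0.4 are assumptions, because the documents give no values. Regressing F on A and S gives:

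- coefficient of S = −r
- arm effect on S = 0.5 − rd
- apparent indirect effect = −r(0.5 − rd)
- apparent direct effect = d + r(0.5 − rd)

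| r | d = 0: indirect / direct | d = −0.5: indirect / direct |
|---|---|---|
| 0.2 | −0.10 / +0.10 | −0.12 / −0.38 |
| 0.3 | −0.15 / +0.15 | −0.195 / −0.305 |
| 0.4 | −0.20 / +0.20 | −0.28 / −0.22 |

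The true indirect effect is zero throughout. With d = −0.5, the share of the effect wrongly credited to self-efficacy is 0.12/0.5 = 24%, 0.195/0.5 = 39% and 0.28/0.5 = 56%.

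**4. How often this reaches significance.** Simulation with N = 68 and two-sided level 0.10 (the plan does not state sidedness). The Sobel statistic is z = ab/√(a²s_b² + b²s_a²), with a the arm effect on S, b the coefficient of S, and s_a and s_b their standard errors. Repeat runs differ by up to about three points.

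| r | Sobel falsely significant, d = 0 | Sobel falsely significant, d = −0.5 |
|---|---|---|
| 0.2 | about 17% | about 24% |
| 0.3 | about 34% | about 53% |
| 0.4 | about 51% | about 78% |

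With d = 0 and no reverse effect the rate is about 2%. A simplified sequence (Steps 1, 2 and 5 plus a significant self-efficacy path) is met in about 1% to 5% of trials with d = 0 and 13% to 41% with d = −0.5.

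**5. The same check on the PA step.** Fatigue was made to drive self-efficacy, self-regulation and PA, with no path back and a 0.5 SD intervention effect on all three. For reverse effects of −0.2, −0.3, −0.4 and −0.5, the Step 4 PA coefficient was significant in 46%, 73%, 89% and 96% of trials, and the Sobel test through PA in 17%, 31%, 44% and 53%. A genuine forward effect of −0.4 gave Step 4 significance in 87%, so Step 4 cannot tell the two apart. All five steps were met in 0.4% to 3% of these reversed trials. They were met in 0.6% to 15% when the intervention instead acted only on fatigue (−0.5 SD), against 9% under the forward model.

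**The case against.** Section 4 calls this an exploratory pilot, and Section 6 says that the model describes relationships. Measuring mediators only before and after is a common pilot trade-off, and the plan applies it consistently. Associations can be described from these data. All of this stands, and it limits the point to interpretation.

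Step 1 also gives some protection. If the intervention does nothing to fatigue, Step 1 passes in only about 10% of trials, so the full sequence is rarely met. The protection weakens if the intervention lowers fatigue by a route outside the model. The Sobel test is not stated to depend on Step 1.

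A reader might infer that Aim 1 cannot be answered at all. The documents do not support that: the t-tests on self-efficacy and self-regulation, and the regressions on arm in Steps 1 and 2, compare randomised groups.

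A reader might also take the rate at which the single self-efficacy-to-fatigue coefficient is significant (about 50%, 80% and 96% for r = 0.2, 0.3 and 0.4) as the rate of false mediation claims. Those figures are largely the power to detect the correlation that was assumed, and that coefficient alone is not the plan's criterion.

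**Conclusion.** The point holds for Steps 3 to 5 and the Sobel test only. The timing is clear from the Study Calendar and Sections 3 and 5. The fatigue-to-activity path is the protocol's own, while the fatigue-to-score path is an inference. Under the assumed reverse correlations, the Sobel test is falsely significant far more often than the 2% seen without reversal, and the step sequence misleads mainly when the intervention lowers fatigue by another route. The rates rest on assumed effect sizes, and the self-efficacy simulation omits self-regulation and PA, so they show plausible size and do not predict what this trial will find.

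It would also go too far to say that an extra survey at Visit 4 resolves the matter, because PA would still be recorded after the Visit 6 fatigue score. In an exploratory pilot this is a should-fix matter of what may be concluded.

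**What to change.** **Core change, wording only.** In Section 6, Specific Aim 1, remove the Step 5 conclusions that the effect is indirect or direct, and the reading of the Sobel test as proof of mediation. State instead that Steps 3 to 5 and the Sobel test describe associations among measures taken at about the same time, and do not establish that self-efficacy, self-regulation or PA changes fatigue. Carry the same limit into Aim 2, which reuses the model. The cost is a few sentences and a more modest claim.

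**Optional, partial remedy.** Give the two process scales and the PROMIS Fatigue Short Form to both arms at Visit 4, before the facilitator session. Use the Visit 4 process scores as lagged mediators of Visit 6 fatigue, with Visit 4 fatigue as covariate. In simulation this returns the false self-efficacy path rate to about 10%, the nominal level, if reverse effects act only on the same day and fatigue is measured without error. With an assumed reliability of 0.7 to 0.8 it is 11% to 17%.

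The costs are some survey burden and a mediator contrast that reflects only the sessions at Visits 2 and 3. (The Study Calendar puts the initial education at Visit 1 and Section 5 puts it at Visit 2; these should be reconciled.) The PA-to-fatigue step would remain unrepaired, so the wording change is needed in either case.

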Specific Aim 2: To determine the preliminary efficacy of the PA intervention on outcome variables of PA (steps/day by accelerometer) and fatigue severity, data analysis will examine differences in baseline and post-study measures of PA (steps/day by accelerometer) and fatigue severity (PROMIS-29 and PROMIS Fatigue scores) for each group. Group differences will then be compared using t-tests to detect the effect of the PA intervention on these outcomes. Direct and indirect effect of the intervention on fatigue severity will be studied using the mediation model discussed in Aim 1. Quantitative data about the fidelity of the intervention will be used to estimate the dose of the delivered intervention for each participant and to explore whether there was a dosage effect on the outcomes.

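### Aim 1 mediation rules (reused in Aim 2): Steps 1 and 5 can mislabel a real indirect effect, and no product test of the serial path is defined

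*Combined protocol and SAP*

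**What the plan says.** Section 6, Specific Aim 1, sets up a serial model. Self-efficacy and self-regulation are the main mediators, PA is the second mediator and fatigue severity is the outcome. It then states: "The direct and indirect effect of treatment on PA and fatigue severity will be determined by the following steps".

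- The first step is "Step 1. The regression of the fatigue severity on the intervention variable, ignoring the mediators, is significant".
- Step 2 is "The regression of the main mediators on the intervention variable is significant". Step 3 asks the same of PA on the main mediators, and Step 4 of fatigue on PA, each with adjustment for what comes earlier in the chain. Nothing says whether one main mediator or both must pass.
- Step 5 concludes *indirect* if the intervention coefficient, "controlling for the mediators, is non-significant and nearly-zero". If that coefficient, "controlling for the mediators, is still significant, then the effect of treatment on fatigue severity is direct".
- The coefficients named for calculation are those for the "associations between the intervention variable and the mediators as well as between the fatigue severity and the mediators". Then: "The Sobel test will be used to test if the mediation effect is statistically significant".

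Aim 2 adds: "Direct and indirect effect of the intervention on fatigue severity will be studied using the mediation model discussed in Aim 1". The relationships of self-efficacy and self-regulation to PA and fatigue are part of the primary objective in the Protocol Summary.

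**The concern.** There are four difficulties.

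1. A total effect passed along three links is the product of three paths and is usually small. A requirement that it be significant can reject a chain whose links are all real.
2. A significant adjusted coefficient shows that a direct effect exists. It does not show that an indirect one is absent. A non-significant coefficient in a small trial does not show a direct effect of zero. Step 5 draws both inferences. It has no outcome for both effects together, and none for a coefficient that is non-significant but not close to zero.
3. The link from self-efficacy and self-regulation to PA makes the model serial. It is estimated in Step 3 but is missing from the coefficients listed before the Sobel test, and no product is defined. The indirect effect on PA, also promised, has no product test either.
4. The choice between one and both mediators changes the error rates and is left open.

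At stake is the mediation conclusion. The report could say *no mediation* or *direct* although the proposed mechanism is operating. The Sobel path, the mediator rule and the near-zero limit could also be chosen after the results are seen.

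**Working it through.** **Inputs from the plan (section 6, Sample Size):** 68 analysed, 34 per group, 4 predictors, medium effect, significance level 0.10, power 80%. **Assumed:** two-sided tests; 0.10 also applies to the steps; medium means f² = 0.15 or d = 0.5. The documents give no path sizes.

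**1. The plan's own figure.** Overall F test, u = 4, v = 68 − 5 = 63, noncentrality 0.15 × 68 = 10.2: power 79.6% (80.2% at 69). The figure of 68 reproduces, for an overall R² test.

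**2. Step 1 at that size.** It has one predictor, so it is a two-group comparison with noncentrality d × √(34/2). At d = 0.5 this is 2.06 and power is 65%. Power of 80% needs d = 0.61.

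**3. Total effect carried by a chain.** With standardised paths a (intervention to each mediator, groups coded ±1), d (mediator to PA) and b (PA to fatigue), the group difference in fatigue is 2 × (2 × a × d × b). Take a = 0.243, equivalent to d = 0.5 because 0.5/√(0.25 + 4) = 0.243, or a = 0.36. Take the other paths as 0.36, equivalent to f² = 0.15 because √(0.15/1.15) = 0.36.

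- a = 0.243: 4 × 0.243 × 0.36 × 0.36 = 0.126 SD, Step 1 power 14.5%.
- a = 0.36: 4 × 0.36 × 0.36 × 0.36 = 0.187 SD, Step 1 power 19.7%.

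**4. Simulation** (4,000 trials per row, alpha 0.10, Step 5 counted as non-significance only). Figures are % of trials. *Serial sum* means that the 90% Monte Carlo interval for the sum of the two three-path products excludes zero. SE is self-efficacy.

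| Assumed truth | Step 1 | Steps 2–4, one mediator | Steps 2–4, both | All five, one / both | Serial sum | Sobel via SE | Sobel via PA |
|---|---|---|---|---|---|---|---|
| Fully serial, a = 0.243 | 14.9 | 70.8 | 31.8 | 6.9 / 3.8 | 68.3 | 2.3 | 21.4 |
| Fully serial, a = 0.36 | 20.2 | 79.3 | 60.9 | 11.5 / 9.2 | 79.7 | 5.5 | 41.2 |
| As row 1, mediator residuals correlated 0.5 | 13.8 | 59.3 | 32.5 | 5.6 / 3.8 | 53.8 | 2.4 | 18.4 |
| As row 2, mediator residuals correlated 0.5 | 19.7 | 72.7 | 52.9 | 10.7 / 8.1 | 72.3 | 5.2 | 36.1 |
| As row 1, mediators also to fatigue 0.25 each | 45.1 | 77.5 | 34.4 | 34.4 / 19.3 | 75.7 | 31.3 | 27.9 |
| As row 2, mediators also to fatigue 0.25 each | 74.3 | 89.0 | 68.0 | 61.9 / 49.5 | 89.6 | 55.4 | 51.1 |
| Fully serial, all paths 0.5 | 67.8 | 87.0 | 87.0 | 53.1 / 53.0 | 87.8 | 9.2 | 84.3 |

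A percentile bootstrap gives 66.9% and 78.3% for the serial sum in the first two rows. The Sobel test via self-efficacy multiplies the intervention-to-SE path by the SE-to-fatigue path adjusted for PA. The second factor is zero in a fully serial chain, so the test almost never rejects. The Sobel test via PA does respond, but it skips the self-efficacy and self-regulation link.

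**5. One or both mediators.** If the intervention moves neither mediator, the chance that at least one Step 2 test is significant is 1 − 0.9² = 19%. After Steps 3 and 4 the one-mediator rule still passes in 14.1% (d = b = 0.36) to 17.7% (d = b = 0.5). The serial sum rejects in 6.8% to 8.5% (bootstrap 7.3% to 9.3%). The both-mediators rule loses power in the first six rows of the table.

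**6. Step 5.**

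- Chain plus a true direct path of 0.20 to 0.30 (group difference 0.4 to 0.6 SD): Steps 2–4 pass and the label is *direct* in 37% to 68% (one mediator) or 16% to 50% (both).
- Full mediation: the mean 90% half-width for the direct group difference is 0.41 to 0.44 SD.
- Full mediation, with near-zero taken as under 0.2 SD: no label applies in 31% to 35%. At 0.1 SD this is 57% to 59%, and at 0.3 SD 12% to 15%.

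**The case against.** The strongest reply is that Steps 2 to 4 already test every link and so act as an informal joint check. This stands. If one mediator suffices, they pass in 70.8% and 79.3% of trials in the two base scenarios, against 68.3% and 79.7% for the serial sum, so no power is lost. A reader might infer that the plan has no test of the chain at all, and the documents do not support that. What is missing is a test of the serial effect as a product. The one-mediator rule that keeps the power also exceeds the nominal 10% when the intervention moves neither mediator.

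A reader might also infer that the analysis stops when Step 1 fails. The plan does not say so. The model is introduced as descriptive, there is no stop rule, and the Sobel sentence carries no condition. The wording that the steps determine the effects makes a condition the natural reading, but not the only one. The low all-five rates apply only on that reading.

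The worst figures come from chosen paths. This also stands. With all paths at 0.5, Sobel via PA reaches 84% against 88%. If the mediators also act on fatigue (0.25 each), a Sobel test summed over both mediators reaches 66% and 85% against 76% and 90%. When a real direct path exists, the label *direct* is incomplete rather than false. Under full mediation, a significant direct coefficient after Steps 2–4 pass is uncommon (6.5% to 8.6%, one mediator).

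Nor does the point show that the sample size is wrong, since 68 reproduces for the test it was computed for.

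**Conclusion.** The point holds and should be fixed, with limited impact. From the text alone:

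- Step 5 draws two inferences that do not follow.
- The Sobel path is unnamed, and the coefficient list omits the link that makes the model serial.
- The mediator rule is open.
- Step 1, if applied as a condition, can reject a real chain.

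The sizes rest on assumed paths, two-sided alpha 0.10 and 68 analysed participants. Under fully serial paths of 0.24 to 0.36, Step 1 is met in about 15% to 20% of trials. The loss is much smaller with paths near 0.5 or with mediators that also act directly on fatigue, though Step 1 then still passes less often than the serial sum. A direct difference is known only to about ±0.4 SD, so non-significance cannot establish a wholly indirect effect.

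The consequence is confined to the mediation conclusions of a study that section 4 calls an exploratory pilot. The t-tests in both aims are unaffected.

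**What to change.** - Keep the Step 2 to 4 regressions as description. State that Steps 1 and 5 are not conditions for concluding mediation, and do not use one mediator passing Steps 2 to 4 as the decision rule.
- Base the mediation result on the serial indirect effects: via self-efficacy (a1 × d1 × b), via self-regulation (a2 × d2 × b) and mainly their sum. Give each a 90% percentile-bootstrap interval (for example 5,000 resamples) in place of the Sobel test. If multiple imputation is used, take a Monte Carlo interval from the pooled coefficients and covariances.
- Report the indirect effect on PA (a1 × d1, a2 × d2 and their sum) in the same way.
- Report total and direct effects with 90% intervals. Replace the Step 5 labels with a statement that both effects can be present, that a significant direct effect does not exclude an indirect one, and that non-significance does not show zero.
- State that post-study PA is recorded in the week after the Visit 6 surveys (section 5), which include fatigue. The PA-to-fatigue path is then an association and not proof of order, which no choice of interval can cure.
- Say that the same rules apply in Aim 2.

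Cost: revised wording and a little more analysis work, with no new data or participants. The plan expects 10% attrition and considers imputation from 5% missing, so the interval may have to be combined with imputation. The team should confirm that its SPSS set-up can do this.
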